## **7.6. Efficacy Analysis**

All Efficacy analyses are performed for efficacy population.

**7.6.1. FLT3 mutation negative Composite Complete Response (CRc) rate in induction**

This is primary endpoint. The composite complete response includes CR and CRi. Subjects who are FLT3 mutation negative by PCR at the end of induction and response of CR or CRi are counted as responders in this analysis. The rates are derived from responders over each treatment arms.

The final analysis of FLT3 mutation negative CRc rate will be performed after the last patient has completed the induction treatment and all patients have MRD response data available. Patients who drop out prior to MRD response assessment will be counted as non-responders in the analysis. The FLT3 mutation negative CRc rate will be compared between gilteritinib and midostaurin arms using Fisher's exact test. All eligible and treated patients will be included into the analysis. Two-sided 90% confidence interval on the difference in the FLT3 mutation negative CRc rate will be provided based on the normal approximation to the difference of two independent binomial proportions with continuity correction.

Multivariable logistic regression modeling will be used to adjust for the stratification factors and other possible baseline clinical and biological risk factors (eg, age, WBC, hemoglobin, platelet, disease categories, and cytogenetics).

Comparison of CRc rate between treatment arms will also be conducted in patients with de novo AML, t- AML and AML-MRC separately; and in patients with favorable, intermediate, and adverse risk separately, determined by 2017 ELN risk classification.

composite responder = FLT3 mutation negative and response CR or CRi after induction treatment

responder rate = responder / all efficacy population

composite responder rate in arm A = responder in arm A / arm A efficacy

population composite responder rate in arm B = responder in arm B / arm B efficacy population

A sensitivity analysis will also be done among those with MRD assessment after induction

responder rate = responder / (all efficacy population subject – subject dropouts prior to MRD assessment) composite responder rate in arm A = responder in arm A / (arm A – subjects' dropout prior to MRD assessment) composite responder rate in arm B = responder in arm B / (arm B – subjects' dropout prior to MRD assessment)

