#### **ARM B (7+3) + Midostaurin**

- **Cytarabine** 100 mg/m^2/day will be administered by continuous IV infusion for a total of 7 days beginning Day 1
- **Daunorubicin** 90 mg/m^2/day will be administered IV per package insert or per institutional guidelines or over 30-60 minutes Days 1,2,3.
- **Midostaurin** 50 mg orally BID x 14 days beginning on day 8

If there is a delay in starting FLT3 inhibitors in Arm A or Arm B (due to obtaining drug, i.e. insurance, formulary, etc.), the FLT3 inhibitor will need to stop after Day 21 dose (i.e., Day 21 or Day 22 [if FLT3 inhibitor started on Day 9]). No missed doses will be made up.

**NOTE:** If second cycle of induction is needed, daunorubicin dose will be decreased to 45 mg/m^2/day IV Days 1,2,3.

---

A bone marrow aspirate/biopsy will be performed on all patients on Day 21 (+/-1 day window; delays due to holidays, weekends, or other unforeseen circumstances will be permitted) to determine the need for a second induction cycle. If the marrow aspirate/biopsy is inadequate to make a determination, consider repeating the bone marrow assessment in 5-7 days.

**Arm A + Gilteritinib:** If second cycle of induction is planned, treatment will begin after Day 28 (i.e.,  $\geq 7$  days after completing gilteritinib) but no later than Day 45.

**Arm B + Midostaurin:** If second cycle of induction is planned, treatment will begin after Day 24 (i.e.,  $\geq 3$  days after completing midostaurin) but no later than Day 45.

A repeat bone marrow aspirate/biopsy should be done to assess for response and MRD status upon peripheral blood count recovery (Absolute Neutrophil Count (ANC)  $\geq 1000/\text{mm}^3$ , platelets  $\geq 100,000/\text{mm}^3$ ) but no later than Day 60 after initiation of the first cycle of induction therapy for patients who receive 1 cycle of induction or no later than Day 60 after initiation of the second cycle of induction therapy (i.e., Day 84-105) for patients who receive 2 cycles of induction (MRD sample will be obtained by Day 60 on all patients even if counts have not recovered. The only exception is a patient who has been declared a relapse based on blood counts).

Patients who do not achieve a CR or CR with incomplete hematologic recovery (CRi) by Day 60 if one cycle and Day 84-105 if 2 cycles of induction therapy will be removed from study.

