## Statistical Analysis Plan

Study code PrE0905

Version Final V3

Date 09 November 2023

transplant after induction or after 0-4 cycles of chemotherapy consolidation. The primary objective of this study is to assess the FLT3 mutation negative CRc (includes CR and CRi) rate of patients who receive arm A gilteritinib compared to those who receive arm B midostaurin in addition to standard therapy with cytarabine and daunorubicin after induction. FLT3 mutation negativity is evaluated by PCR at the end of induction.

We assume with the control arm of cytarabine, daunorubicin and midostaurin (arm B), the FLT3 mutation negative CRc rate after induction is 40%. With 170 eligible patients with allocation ratio of 1:1 to the two arms, the study will have 80% power to detect an improvement of 20% in the FLT3 mutation negative CRc rate in the arm A gilteritinib arm (i.e., from 40% to 60%) at the one-sided significance level of 0.05 based on Fisher's exact test.

Accounting for 5% ineligibility, we will need a total of 179 patients.

Assume 7 FLT3 mutated patients will be accrued each month, the accrual of the study will be completed in 2.1 years.

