### 7.3. Endpoints

#### 7.3.1. Primary Endpoint

The primary endpoint of this study is the FLT3 mutation negative (evaluated by polymerase chain reaction [PCR]) Composite Complete Response (CRc) [includes CR and CRi] rate after induction treatment and complete MRD assessment. The cut points used for FLT3 mutation negative are 1% (equivalent to  $10^{-2}$ ) for FLT3-TKD and  $10^{-4}$  for FLT3-ITD.

The final analysis of FLT3 mutation negative CRc rate will be performed after the last patient has completed the induction treatment and all patients have MRD response data available. Patients who drop out prior to MRD response assessment or without MRD assessment will be counted as non-responders in the analysis. The FLT3 mutation negative CRc rate will be compared between gilteritinib and midostaurin arms using Fisher's exact test. All eligible and treated patients will be included into the analysis. Two-sided 90% confidence interval on the difference in the FLT3 mutation negative CRc rate will be provided based on the normal approximation to the difference of two independent binomial proportions with continuity correction.

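### The sensitivity analysis of the primary endpoint drops early deaths and other unsampled failures along with truly missing MRD, so it is biased whenever these losses differ between arms

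*SAP*

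**What the plan says.** The primary endpoint requires both CR or CRi and FLT3 mutation negativity at the end of induction. For the main analysis, SAP 7.3.1 states: "Patients who drop out prior to MRD response assessment or without MRD assessment will be counted as non-responders in the analysis". SAP 7.6.1 uses the whole efficacy population of each arm as the denominator.

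SAP 7.6.1 then adds: "A sensitivity analysis will also be done among those with MRD assessment after induction". The formula beneath that sentence divides responders by the arm's efficacy population less its dropouts before MRD assessment. *Dropout* is not defined, and no reason for leaving is exempt. SAP 4.4.2 lists death, unacceptable adverse events, non-protocol therapy and failure to reach CR/CRi among the reasons for stopping treatment.

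Protocol 5.2.1 requires an MRD sample by Day 60 from all patients, including those whose counts have not recovered. It allows one waiver: "The only exception is a patient who has been declared a relapse based on blood counts". Protocol section 9 and footnote 17 of the Protocol section 10 table repeat the rule.

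**The concern.** A sensitivity analysis for missing MRD should ask how far the result depends on patients whose outcome is unknown. A patient who died before the marrow, or whose disease is back in the blood, is not in CR/CRi at that assessment. That patient is a non-responder whatever an MRD test would have shown. The uncertainty lies elsewhere: in patients in CR/CRi without a valid FLT3 result, and in patients who are alive but withdrew with no marrow assessment.

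The SAP formula treats both groups alike and deletes both. Membership of the resulting set depends on what happened after randomisation, so the comparison is no longer between randomised groups. If one arm loses more unsampled failures, its rate rises because its failures have left the denominator. This is the only sensitivity analysis specified for missing MRD on the primary endpoint, in an open-label trial, so readers are likely to judge robustness by it.

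The wording has a second problem. The sentence restricts to patients with an MRD assessment, while the formula removes dropouts. SAP 7.3.1 names these as separate groups. A CR/CRi patient with an inadequate sample who did not drop out is excluded by the sentence and kept by the formula, so two programmers could report different rates.

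**Working it through.** **Inputs from SAP 4.1.** Control rate: "the FLT3 mutation negative CRc rate after induction is 40"%. Effect: "i.e., from 40% to 60"%. Test: "at the one-sided significance level of 0.05 based on Fisher's exact test". Size: "With 170 eligible patients with allocation ratio of 1:1 to the two arms", so 85 per arm. The documents give no rate of missing MRD, so all counts of removed patients below are assumptions.

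**The plan's own figure.** The SAP says "the study will have 80% power to detect an improvement of 20" points. Full enumeration of two binomials (85 per arm, 60% versus 40%) with a one-sided Fisher test at 0.05 gives 80.6% power. The total also reproduces: 170/(1 − 0.05) = 179. The design, which uses the full denominator, is sound.

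**Formulas.** With r responders and m patients removed in an arm of 85, the primary rate is r/85 and the sensitivity rate is r/(85 − m). All removed patients are assumed to be non-responders. Arm A is gilteritinib, arm B midostaurin; p is one-sided Fisher, favouring A.

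| Responders A, B | Removed A, B | Primary rates | p | Sensitivity rates | p |
|---|---|---|---|---|---|
| 38, 38 | 15, 5 | 44.7% vs 44.7% | 0.56 | 38/70 = 54.3% vs 38/80 = 47.5% | 0.25 |
| 42, 38 | 15, 5 | 49.4% vs 44.7% | 0.32 | 42/70 = 60.0% vs 38/80 = 47.5% | 0.086 |
| 42, 38 | 10, 5 | 49.4% vs 44.7% | 0.32 | 42/75 = 56.0% vs 38/80 = 47.5% | 0.18 |
| 42, 38 | 5, 5 | 49.4% vs 44.7% | 0.32 | 42/80 = 52.5% vs 38/80 = 47.5% | 0.32 |
| 34, 34 | 9, 9 | 40.0% vs 40.0% | 0.56 | 34/76 = 44.7% in both | 0.56 |
| 34, 34 | 9, 17 | 40.0% vs 40.0% | 0.56 | 34/76 = 44.7% vs 34/68 = 50.0% | 0.79 |
| 51, 34 | 9, 26 | 60.0% vs 40.0% | 0.007 | 51/76 = 67.1% vs 34/59 = 57.6% | 0.17 |

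The first row creates a difference of 6.8 points from none. The last shrinks 20.0 points to 9.5. Equal removal from arms with equal response leaves the difference at zero. If nobody is removed, the sensitivity and primary results are identical.

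**Error rate when the arms are truly equal.** Simulation: 40,000 trials, 85 per arm, 40% response in both arms, every patient without MRD a non-responder. The chance of one-sided p ≤ 0.05 favouring gilteritinib in the sensitivity analysis:

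| Missing MRD, A vs B | Sensitivity analysis |
|---|---|
| 10% vs 10% | 3.6% |
| 15% vs 10% | 7.0% |
| 20% vs 10% | 12.8% |
| 30% vs 10% | 36.5% |
| 10% vs 20% | 0.7% |

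The primary analysis stayed at about 3.5% to 3.7% throughout.

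**The case against.** The strongest reply is that nothing is decided on this analysis. The primary test keeps all eligible and treated patients and counts those without MRD as non-responders. The sample size and the interim rule in SAP 7.7 rest on the primary endpoint, and the sensitivity analysis is openly labelled with its formula printed. That stands: the harm is to interpretation, not to the planned test.

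A reader might infer that refractory patients are removed as a class, and hence that the analysis rewards the arm with more induction failures. The documents do not support this. The protocol requires a sample by Day 60 even without count recovery, so a sampled refractory patient remains as a non-responder. Only failures that go unsampled are lost.

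A reader might also count every toxicity withdrawal as a known failure. Protocol 7.3 asks that patients who stop early be followed for response where possible, so stopping treatment does not by itself mean no MRD. A living patient who withdrew with no marrow has an unknown outcome.

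The scenarios are chosen, and some are marked. A split of 15/85 versus 5/85 is itself unlikely by chance (two-sided Fisher p = 0.03) and would show in the disposition table. None of the shifts in the counts table takes p from above 0.05 to below it. This limits the claim about size but not about the mechanism.

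Finally, excluding only CR/CRi patients without a valid result also conditions on a post-randomisation outcome. That is fair, and it is why the tipping-point form is preferable to exclusion.

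**Conclusion.** The point holds in limited form. As printed, the SAP 7.6.1 sensitivity denominator removes early deaths and other documented failures without an MRD sample, although these are known non-responders. The estimate is biased when such losses differ between arms, and the bias can flatter or penalise either drug. It does not always favour gilteritinib.

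The size depends on quantities the documents do not give. Under the assumption that all removed patients are non-responders, imbalances of 15 versus 5 or 9 versus 26 move the difference by roughly 7 to 10 points. With arms truly equal, 15% to 30% missing on gilteritinib against 10% on midostaurin raises the chance of a nominally significant sensitivity result to between 7.0% and 36.5%. If every failure is sampled as the protocol asks, the problem largely disappears.

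The primary analysis is unaffected. This is a faulty robustness check that is cheap to correct, not a flaw in the trial's main inference.

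**What to change.** In SAP 7.6.1:

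- Define *dropout*, and make the sentence and the formula describe the same set of patients.
- Keep deaths before assessment, relapses and all patients documented as not in CR/CRi in the denominator as non-responders.
- Treat as missing only patients whose FLT3-negative CRc status is truly unknown: those in CR/CRi without a valid FLT3 MRD result, and those alive and withdrawn with no marrow assessment.
- Vary the outcomes of that group separately by arm in a tipping-point analysis. If a simpler version is wanted, exclude only that group and say so.
- Tabulate missing MRD by arm and reason.

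The cost is SAP wording, one derivation flag and a small table, with no new data. The downside is a little more derivation work and a result likely to lie closer to the primary analysis, particularly if few patients in CR/CRi lack a sample, since the protocol requires one before consolidation.

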**7.6.2. FLT3 mutation negative Complete Response (CR) rate in induction**

This is one of secondary endpoints. The FLT3 mutation negative Complete Response (CR) rate of patients with FLT3 mutated AML who receive gilteritinib will be compared to those who receive midostaurin in addition to standard therapy with cytarabine and daunorubicin during induction.

responder = FLT3 mutation negative and response CR after induction

treatment responder rate = responder / all efficacy population

responder rate = responder in arm A / arm A efficacy

population responder rate = responder in arm B / arm

B efficacy population

The final analysis of FLT3 mutation negative CR rate will be performed after the last patient has completed the induction treatment and all patients have MRD response data

## Statistical Analysis Plan

Study code PrE0905

Version Final V3

Date 09 November 2023

available. Patients who drop out prior to MRD response assessment will be counted as non-responders in this analysis. The FLT3 mutation negative CR rate will be compared between gilteritinib and midostaurin arms using Fisher's exact test. Two-sided 90% confidence interval on the difference in the FLT3 mutation negative CR rate will be provided based on the normal approximation to the difference of two independent binomial proportions with continuity correction.

Multivariate logistic regression modeling will be used to adjust for the stratification factors and other possible baseline clinical and biological risk factors (eg, age, WBC, hemoglobin, platelet, disease categories, and cytogenetics).

### **7.6.3. MRD- (evaluated by flow) CRc rate**

The MRD- CRc responders are subjects who respond CR or CRi and MRD response is negative as evaluated by flow.

The MRD- CRc rate will be compared by 2 treatment arms using Fisher's exact test. Two-sided 90% confidence interval on the difference in the MRD- CRc rate will be provided based on the normal approximation to the difference of two independent binomial proportions with continuity correction.

Multivariate logistic regression modeling will be used to adjust for the stratification factors and other possible baseline clinical and biological risk factors (eg, age, WBC, hemoglobin, platelet, disease categories, and cytogenetics).

### **7.6.4. CRc (CR or CRi) Rate**

The CRc (CR or CRi) rates will also be compared between 2 treatment arms by using Fisher's exact test. Two-sided 90% confidence interval on the difference in the CRc rate will be provided based on the normal approximation to the difference of two independent binomial proportions with continuity correction.

Multivariate logistic regression modeling will be used to adjust for the stratification factors and other possible baseline clinical and biological risk factors (eg, age, WBC, hemoglobin, platelet, disease categories, and cytogenetics).

### **7.6.5. FLT3 mutation negative CRc (CR or CRi) ate after first consolidation cycle**

This analysis is for the patients who are FLT3 mutation positive after induction and administered consolidation. The CRc (CR or CRi) rates will also be compared between 2 treatment arms by using Fisher's exact test. Two-sided 90% confidence interval on the difference in the CRc rate will be provided based on the normal approximation to the difference of two independent binomial proportions with continuity correction.

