## 12 Statistical Considerations

### 12.1 Study Design & Sample Size Considerations

This is a randomized, open-label Phase II study comparing gilteritinib to midostaurin in patients receiving standard induction therapy with cytarabine and daunorubicin in FLT3 mutated AML. Patients will be stratified according to FLT3-TKD vs. FLT3-ITD mutation. Patients with FLT3-ITD mutation will undergo further stratification with NPM1 mutation status (positive vs. negative) and signal ratio (high [ $\geq 0.5$ ] vs. low [ $<0.5$ ] of FLT3 Wild Type). Patients will be randomized to receive standard induction treatment (cytarabine and daunorubicin) with either gilteritinib or midostaurin. If achieving CR or CRi, these patients will go on to receive standard consolidation treatment of high-dose cytarabine with the study drug received during induction (gilteritinib or midostaurin). Patients may proceed to allogeneic transplant after induction or after 0-4 cycles of chemotherapy consolidation. The primary objective of this study is to assess the FLT3 mutation negative CRc (includes CR and CRi) rate of patients who receive gilteritinib compared to those who receive midostaurin in addition to standard therapy with cytarabine and daunorubicin after induction. FLT3 mutation negativity is evaluated by PCR at the end of induction.

Based on a retrospective study performed at John-Hopkins, we assume with the control arm of cytarabine, daunorubicin and midostaurin, the FLT3 mutation negative CRc rate after induction is 40%. With 170 eligible patients with allocation ratio of 1:1 to the two arms, the study will have 80% power to detect an improvement of 20% in the FLT3 mutation negative CRc rate in the gilteritinib arm (i.e., from 40% to 60%) at the one-sided significance level of 0.05 based on Fisher's exact test. Accounting for 5% ineligibility, we will need a total of 179 patients.

Assume 7 FLT3 mutated patients will be accrued each month, the accrual of the study will be completed in 2.1 years.

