The final analysis of EFS and OS will be performed when the full information of EFS is reached (i.e., 110 events have occurred). Estimates of EFS and OS, including medians and confidence intervals, will be calculated using the Kaplan-Meier method. Comparison of EFS and OS between treatment arms will be conducted using the one-sided stratified log-rank test with FLT3 mutation (TKD vs ITD), FLT3-ITD mutation signal ratio (high  $\geq 0.5$  vs. low  $<0.5$  of FLT3 Wild Type), and NPM1 mutation status, the same stratification factors used in randomization. Cox proportional hazards models, stratified on the same factors above, will also be used to assess the treatment effect.

A sensitivity analysis of EFS will be performed where follow-up will be censored at the start of transplantation.

Comparison of CRc rate, EFS and OS between treatment arms will also be conducted in patients with de novo AML, t-AML and AML-MRC separately; and in patients with favorable, intermediate, and adverse risk separately, determined by 2017 ELN risk classification.

To determine the predictive value of Minimal Residual Disease (MRD) positivity and negativity post induction therapy. EFS and OS of the patients who achieved MRD negative after induction will be compared with those who did not. All CRc patients who have MRD response evaluated post induction will be included into this analysis. The interaction of treatment and MRD status will be tested in the Cox regression model. If a strong interaction effect is detected, the treatment effect will be looked at within MRD+ and MRD- patients separately.

The correlation between MRD by molecular studies and morphology will be assessed. McNemar's test will be used to assess the concordance of the measurements.

For patients who are FLT3 mutation positive after induction and administered consolidation, the FLT3 mutation negative CRc rate after first cycle of consolidation and their corresponding 90% confidence intervals will be given by treatment arm.

To assess the correlation of FLT3 mutation with outcome, the EFS and OS of those patients with FLT3-TKD mutation will be compared with patients with FLT3-ITD mutation. Among those patients with FLT3-ITD mutation, EFS and OS will be compared among those with ITD signal ratio >0.5 with those ≤ 0.5 of FLT3 Wild Type.

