## 8. SUMMARY OF CHANGES FROM PROTOCOL-SPECIFIED ANALYSES

No changes are planned.

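### SAP 7.6.5 adds an undeclared between-arm test in a subset formed after randomization, and its heading and body name different endpoints

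*SAP*

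**What the plan says.** Protocol 12.2.2 takes the patients who remain FLT3 mutation positive after induction and go on to consolidation. It plans their FLT3-negative CRc rate after the first consolidation cycle and says that "their corresponding 90% confidence intervals will be given by treatment arm". It plans no test and no estimate of the difference between arms. The matching exploratory objective (Protocol 2.3, SAP 3.3) is likewise worded as an evaluation by arm.

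SAP 7.6.5 keeps the same patients but instructs: "The CRc (CR or CRi) rates will also be compared between 2 treatment arms by using Fisher's exact test". It adds a two-sided 90% interval on the difference, by the normal approximation with continuity correction. It gives no significance level, no sidedness and no responder formula. The section heading refers to FLT3 mutation negative CRc; both sentences of the body that describe the analysis refer only to CRc.

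SAP 2.1 says that the SAP supersedes the protocol's statistical section and that substantial differences will be identified. SAP section 8, where they would be listed, says: "No changes are planned".

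**The concern.** Three things are wrong with SAP 7.6.5 as it stands.

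- **Undeclared change.** A descriptive analysis has become a hypothesis test. Because the SAP takes precedence, the test governs, and a reader of section 8 would not know that it had been added.
- **Non-randomized contrast.** A patient enters the subset by reaching CR or CRi, staying FLT3-positive, and receiving consolidation rather than, for example, going directly to transplant. All three happen after randomization, and treatment can affect each. FLT3 clearance in remission is the trial's primary endpoint, so the design hypothesis itself predicts that the subset is selected differently in the two arms.
- **Two endpoints.** The heading and the body disagree. If the body is programmed literally, the table answers a different question from the objective.

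At stake is a p-value that could be taken as evidence about the two drugs in consolidation when it mixes that effect with selection, possibly on an unintended endpoint.

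**Working it through.** **1. The plan's own figure.** Protocol 12.1 states: "With 170 eligible patients with allocation ratio of 1:1 to the two arms, the study will have 80% power", for 40% against 60%, "at the one-sided significance level of 0.05 based on Fisher's exact test". Full enumeration of Fisher's test with 85 per arm gives 80.6% power, so the figure reproduces. The inflation for ineligibility also reproduces: 170 / 0.95 = 178.9, rounded up to 179. Neither document states a size or power for the 7.6.5 comparison.

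**2. Size of the subset.** Inputs from the documents: 85 per arm; FLT3-negative CRc after induction of 40% (midostaurin) and 60% (gilteritinib). Inputs not in the documents, so assumed: overall CRc rate C of 70-90%, equal in both arms; share s of FLT3-positive remitters given consolidation of 50-100%.

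- Midostaurin: n = 85 × (C − 0.40) × s
- Gilteritinib: n = 85 × (C − 0.60) × s

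The last column is the power of a one-sided 0.05 Fisher test for a true 20-point advantage of gilteritinib (30% vs 50%; 40% vs 60%) at the whole-number sizes in parentheses. The level and sidedness are borrowed from the primary test, since 7.6.5 gives none.

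| C | s | Gilteritinib | Midostaurin | Power |
|---|---|---|---|---|
| 70% | 100% | 8.5 (8) | 25.5 (25) | 16%; 15% |
| 70% | 50% | 4.25 (4) | 12.75 (13) | 6%; 5% |
| 80% | 100% | 17 (17) | 34 (34) | 30%; 30% |
| 80% | 50% | 8.5 (9) | 17 (17) | 16%; 17% |
| 90% | 100% | 25.5 (26) | 42.5 (42) | 40%; 38% |
| 90% | 50% | 12.75 (13) | 21.25 (21) | 21%; 20% |

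The ranges are therefore about 4-26 against 13-42 patients, with power of about 5-40%.

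**3. How firm is the imbalance?** Before the consolidation filter, the gap between arms is 85 × [0.20 − (C in gilteritinib − C in midostaurin)]. With equal CRc it is 17 patients. With 75% CRc on midostaurin and 85% on gilteritinib (assumed), the counts are 85 × 0.35 = 29.75 and 85 × 0.25 = 21.25, a gap of 8.5. Unequal groups are probable, but the extent depends on a rate that the documents do not give.

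**4. Can selection alone create a difference?** An illustrative model, not an estimate: rank patients by resistance u from 0 to 1. Those with u below 0.80 reach CRc. Induction clears FLT3 below u = 0.40 on midostaurin and below u = 0.60 on gilteritinib. The chance of clearance in consolidation is 1 − u in both arms, so there is no drug effect in consolidation.

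- Midostaurin subset, u from 0.40 to 0.80: mean clearance 1 − 0.60 = 40%
- Gilteritinib subset, u from 0.60 to 0.80: mean clearance 1 − 0.70 = 30%

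A 10-point deficit for gilteritinib appears with no difference between the drugs in consolidation. The model shows that the mechanism is possible; it does not fix its sign or size in this trial.

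**5. The endpoint.** Protocol 5.2.2 and SAP 4.4.1 both require CR or CRi before consolidation. Read as plain CRc, everyone in the subset has met the endpoint once, and the test can detect only its loss. At 90% vs 97% CRc the power is about 0-12% over the same sizes, and if all patients stay in CRc then p = 1. The sentence quoted from 7.6.5 also stands in 7.6.4, where plain CRc is intended. The likeliest explanation is that the FLT3-negative qualifier was lost when the sentence was reused.

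**The case against.** The best defence is that little depends on this analysis. It is exploratory, it is not in the SAP's list of secondary endpoints, no stopping rule uses it, and it leaves the primary test's power and error rate untouched. The protocol, not the SAP, chose the subset, and restoring per-arm rates still puts two selected groups side by side. One may also argue that a single exploratory test is not a substantial difference under SAP 2.1. All of this limits the weight of the point. It does not remove it: moving from description to a test changes the kind of claim, and the heading and body still conflict.

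Three stronger readings are tempting, and the documents do not support them.

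- **That the test concerns an endpoint already met.** This follows only from the literal body text. The heading and objective 3.3 name FLT3-negative CRc, which no patient in the subset has met, since all are FLT3-positive by selection. Even plain CRc is reassessed after consolidation cycle 1 and can be lost.
- **That the comparison is tilted against gilteritinib.** This needs gilteritinib to clear more FLT3 in induction and the remaining positives to be more resistant. Selection into consolidation is a further step: transplant straight after induction is allowed and treatment is open-label, so this step could act in either direction.
- **That the subset can be given as one pair of numbers.** Overall CRc and the share given consolidation are not in the documents, so only a range under stated assumptions is justified.

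**Conclusion.** The point holds in a limited form. SAP 7.6.5 departs from Protocol 12.2.2 by adding a between-arm Fisher test and an interval on the difference, and section 8 does not say so. The contrast is not protected by randomization, whatever the direction of the bias; if gilteritinib clears more FLT3 in induction, its remaining positives may be the more resistant patients. The heading and body name different endpoints and must be reconciled.

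The comparison would be small and probably unequal, within the ranges shown, which rest on the design rates, equal CRc in the two arms and the assumed share given consolidation. At such sizes a non-significant result would say little. The normal-approximation interval would also be fragile, particularly for a rate near 100%. The consequence is confined to one exploratory result.

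**What to change.** In SAP 7.6.5:

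1. Restore the protocol's analysis: the FLT3 mutation negative CRc rate after consolidation cycle 1, with a 90% confidence interval for each arm.
2. Delete the between-arm Fisher test and the interval on the difference.
3. Change CRc in the body to FLT3 mutation negative CRc, so that it agrees with the heading and objective 3.3.

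With these edits, the statement in SAP section 8 becomes correct for this analysis.

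The cost is a short change of SAP wording, a matching change to the table template if it shows the test, and the loss of one exploratory p-value. Sample size, data collection and the primary analysis do not change. Readers can still compare the two per-arm rates by eye, so the study report should say that the groups were selected after randomization.
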